Primary end point. The primary end point is a composite of renal injury, RRT, and death. Renal injury will be assessed by time-averaged (area under the curve [AUC]) levels of daily SCr for the first 7 days following enrollment. This end point has been used in previous clinical trials conducted in AKI,⁸⁹ and these measurements will be obtained through routine clinical testing. To account for missing data, we will standardize the AUC of daily SCr levels relative to the number of days in which SCr data are available. RRT and death are important confounders of SCr levels, as well as important end points by themselves, and will therefore be considered along with the AUC of SCr levels as part of the primary composite end point. RRT will be defined as receipt of any form of dialysis within the first 7 days of enrollment. Death will be defined as all-cause mortality within the first 7 days of enrollment.

To evaluate the primary composite end point, which includes both continuous (SCr levels) and dichotomous (RRT and death) variables, we will use a rank-based procedure, as prior studies have done,⁹⁰ as follows:

- Patients who die within 7 days of enrollment will be assigned the highest (worst) rank, with no difference in rank assigned to patients who die at different times within the first 7 days.
- Patients who survive >7 days but who require RRT within 7 days of enrollment will be assigned the second highest rank.
- All other patients will be assigned a rank based on the AUC of their SCr, as described above.

Secondary end points. Secondary end points will include new or worsening AKI (defined by KDIGO guidelines);⁹¹ kidney function on hospital discharge (assessed by SCr); hospital- and ICU length of stay; and hospital-, ICU-, and 28-day mortality. We will also evaluate the AUC of urinary injury biomarkers, including KIM-1, NGAL, and IL-18, during the first 5 days using a similar global rank score strategy as described above. Finally, we will evaluate organ-failure free days (assessed by daily SOFA scores) during the first 7 days following enrollment. For the cardiovascular component of the SOFA score, we will use a modified scoring system that has improved accuracy in predicting outcomes,⁹² and for the renal component we will assign a score of “4” (the highest score) to any participant who requires RRT.

C. Statistical methods

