To evaluate the primary end point, we will compare the ranks between treatment groups versus the placebo group with the use of the Wilcoxon Rank Sum test. To evaluate secondary end points, we will compare means and medians between each of the active treatment groups versus the placebo group using parametric (e.g., t-test) and non-parametric (e.g., Wilcoxon Rank Sum) tests, as appropriate. To account for two active treatment groups, we will consider p values <0.025 to be significant for the primary end point. For secondary end points, all of which will be considered exploratory, we will consider p values <0.05 to be significant.

D. Power analysis

150 participants (N=50 per group) will provide >80% power to detect a 0.62 standard deviation difference in the global rank score in each of the active treatment groups vs. placebo, with a two-sided α of 2.5%.

VII. RISKS AND DISCOMFORTS

A. Complications of surgical and non-surgical procedures

Not applicable

B. Drug side effects and toxicities

The only known toxicity of vitamin D metabolites, including calcifediol and calcitriol, is hypercalcemia.^{81 82} Despite an excellent safety profile, transient hypercalcemia has been reported with calcitriol and, to a much lesser extent, with calcifediol. The risks of hypercalcemia in the current study are low, since the planned doses of calcifediol and calcitriol are lower than doses that have been used safely in prior studies in humans (discussed in detail in sections 1E and 1F). Additionally, the following precautions will further minimize risk to patients:

1) Limiting our study to patients with serum total calcium levels ≤ 9.0 mg/dl. Most prior clinical studies of calcifediol and calcitriol (discussed in sections 1E and 1F) were conducted in patients who were generally normocalcemic on enrollment. In contrast, most ICU patients have serum calcium levels in the low-normal range, and many patients (55.2% in one study)⁹³ are frankly hypocalcemic on arrival to the ICU. In the current study, we will exclude patients with serum total calcium levels > 9.0 mg/dl on enrollment (**Table 2**). By limiting enrollment to patients with serum total calcium levels ≤ 9.0 mg/dl, a substantial barrier exists for serum calcium levels to rise into the hypercalcemic range (>10.7 mg/dl) and an even larger barrier for clinically relevant hypercalcemia (>11.5 mg/dl).

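### Length of stay and discharge creatinine are compared directly with no rule for death or RRT; adapting the plan's own rank score would be a cheap improvement

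*Combined protocol and SAP*

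**What the plan says.** Section VI.B lists as secondary end points "kidney function on hospital discharge (assessed by SCr); hospital- and ICU length of stay", alongside ICU, hospital and 28-day mortality. It attaches no rule for death or RRT to the creatinine or stay outcomes. Section VI.C gives the analysis: "we will compare means and medians between each of the active treatment groups versus the placebo group", using a t-test or Wilcoxon test as appropriate. All secondary end points are exploratory, with p<0.05 called significant.

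For the primary end point, VI.B does deal with these events. It states that "RRT and death are important confounders of SCr levels" and sets two tiers: "Patients who die within 7 days of enrollment will be assigned the highest (worst) rank", and "Patients who survive >7 days but who require RRT within 7 days of enrollment will be assigned the second highest rank". Everyone else is ranked by creatinine AUC. The same section analyses the urinary biomarker AUC "using a similar global rank score strategy as described above", and gives any participant on RRT the maximum renal SOFA score. Discharge creatinine and length of stay get no comparable treatment.

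**The concern.** Discharge creatinine is the same analyte as in the primary end point and is open to the same two distortions, yet the safeguard stops short of it. Length of stay has a related problem: death ends a stay, so an early death recorded as a completed stay looks like a quick recovery. Choosing Wilcoxon over the t-test does not help, because a stay of 3 days ending in death still ranks as short.

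At stake is the reading of two secondary comparisons that are tested at p<0.05. A drug that lowered mortality could appear to prolong stay, and a benefit through less dialysis could be largely hidden in discharge creatinine. A mortality difference is not far-fetched on the protocol's own account: section I.B cites a critical-care trial of vitamin D with no overall effect on stay but lower hospital mortality in the severely deficient subgroup.

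**Working it through.** **Plan's own figure.** No power or effect size is given for these end points. The only stated power is for the primary rank score: more than 80% for 0.62 SD with 50 per arm and two-sided alpha of 2.5%. By the normal approximation, 0.62/√(2/50) − 2.241 = 3.100 − 2.241 = 0.859, which gives 80.5%. It reproduces and is not affected by this point.

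**Inputs.** From the documents: 50 per arm, direct comparison, p<0.05. Everything else below is assumed, because the documents give no mortality rate, RRT rate or time to death.

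**1. Stay, all patients included.** Let m be in-hospital mortality, S the survivors' stay and D the decedents' stay.

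Mean stay = (1 − m)·S + m·D, so active minus placebo = (m_placebo − m_active)·(S − D) when the drug changes mortality only.

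Assume S = 15 days, and mortality 25% on placebo and 15% on active.
- D = 5: placebo 0.75×15 + 0.25×5 = 12.5; active 0.85×15 + 0.15×5 = 13.5; the active arm looks 1.0 day worse.
- D = 3: 0.10×12 = 1.2 days.
- D = 8: 0.10×7 = 0.7 days.
- D = 15: no shift. D above 15: the sign reverses.
- Equal mortality: no shift for any D.

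**2. Effect on the Wilcoxon test.** Simulation with 50 per arm and lognormal stays (survivor median 14 days, log-SD 0.7), the drug changing mortality only. The first column of results is the share of trials significantly favouring placebo; chance alone gives 2.5%.

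| Mortality, placebo vs active | Decedent median stay | Direct comparison favours placebo | Death ranked worst: favours active |
|---|---|---|---|
| 25% vs 15% | 3 days | about 12% | about 14% |
| 25% vs 15% | 5 days | about 9% | about 13% |
| 25% vs 15% | 8 days | about 6% | about 14% |
| 25% vs 15% | 14 days | 2.5% | about 14% |
| 40% vs 20% | 4 to 10 days | 28% down to 7% | 41% to 42% |

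At 25% versus 15%, the standard error of the difference in mean stay is about 2.7 to 2.8 days for decedent medians of 3 to 14 days, so a shift of about 1 day is well within sampling noise. With equal mortality (20% in both arms), both methods hold about 5% two-sided error.

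**3. Stay, survivors only.** This removes the short-stay artefact, but it compares groups selected by an outcome that treatment may change. The comparison is then no longer between randomised groups.

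**4. Discharge creatinine.** Let r be the proportion on RRT and v their creatinine. Mean = (1 − r)·1.2 + r·v mg/dl, assuming 1.2 without RRT. RRT falls from 20% to 10%.
- Undialysed value v = 4.0 (notional): 0.10×(4.0 − 1.2) = 0.28 mg/dl lower on active.
- Measured on dialysis, v = 1.5, 2.0 or 2.5: 0.10×0.3 = 0.03, 0.10×0.8 = 0.08, 0.10×1.3 = 0.13.

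So 0.03 to 0.13 of the 0.28 mg/dl is visible. Patients who die have no discharge value. If they are dropped, 25% of placebo and 15% of active patients are missing under the mortality assumed in step 1. If a last value is used instead, it is not a discharge value. The plan does not say which.

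**The case against.** The strongest reply is that the plan is silent rather than wrong. A reader might infer that it prescribes an analysis pointing the wrong way. The documents do not support that: nowhere do they say that decedents' days count as completed stays, or that decedents are dropped for creatinine. This stands, and the point is therefore a missing rule. A rule is still needed, because each available reading (all patients, or survivors only) has a defect.

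Second, the distortion is conditional. It needs unequal mortality and decedents who stay less time than survivors; eligibility also requires that patients be likely to remain alive in the ICU for at least 72 hours. This stands, and it limits the size.

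Third, a reader might infer that these comparisons would drive the decision on a larger trial. Section I.G ties that decision to an effect on AKI, and VIII.B to the immune and inflammatory response; neither names stay or discharge creatinine. Mortality is also reported alongside, so an attentive reader could see the cause of an odd result.

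Fourth, the existing rank scheme cannot be copied, because its tiers cover only death and RRT within 7 days. Section V.A does not list RRT status at discharge among the recorded outcomes. Both are true and are met in the fix.

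Last, ranking death worst turns stay into a composite of death and stay: the 41% to 42% in the table arises although survivors' stays are identical. That is a real drawback, and other rules for death exist. The rank is preferred here because the plan already uses it for the same problem.

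**Conclusion.** The point holds as a gap in two exploratory end points, at minor to moderate importance. As written, VI.B and VI.C leave length of stay open to reversal by early death, or to a non-randomised survivor comparison, and leave discharge creatinine undefined for deaths and flattered by dialysis. The direction for stay follows only if mortality differs and decedents stay less time than survivors. The size, 0.7 to 1.2 days, rests on an assumed 25% versus 15% mortality, a 15-day survivor stay and deaths at day 8 to day 3. The creatinine figures are likewise illustrations. The primary analysis, its alpha and the sample size are untouched. This is a cheap improvement.

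**What to change.** Amend VI.B and VI.C before unblinding, adapting the rank scheme to the time frame of each end point:

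- **ICU stay:** death before ICU discharge takes the worst rank; all others are ranked by ICU days.
- **Hospital stay:** death before hospital discharge takes the worst rank; all others are ranked by hospital days. Neither stay outcome needs an RRT tier.
- **Discharge creatinine:** in-hospital death is worst, on RRT at discharge is next, and all others are ranked by creatinine.

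Compare each active arm with placebo by Wilcoxon. Report survivor-only stay and creatinine, together with mortality, as descriptive. Say in the text that the ranked results are composites that partly reflect mortality.

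The cost is a few sentences plus one field, RRT status at discharge, added to the data listed in V.A. ICU and hospital mortality and length of stay are already listed there.

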Calderol. 25D was formerly available for use in patients as “Calderol”. Calderol was approved by the FDA in 1980 for the treatment of hypocalcemia in patients undergoing chronic renal dialysis. Calderol was withdrawn from the market in 2002 for commercial reasons which were not associated with safety or efficacy of the product.

Royaldee. 25D is currently FDA-approved as “Royaldee” for the treatment of vitamin D deficiency in chronic kidney disease stage 3 or 4 patients with secondary hyperparathyroidism.

Overview of 1,25D

The rationale for evaluating 1,25D as a therapeutic agent in AKI is three-fold: 1) the renoprotective effects of vitamin D metabolites in animal models of AKI were demonstrated exclusively with 1,25D; 2) there may be impaired renal⁵⁹ and extra-renal⁶⁰ conversion of 25D to 1,25D in critical illness due to elevated FGF23⁶¹ or other mechanisms; 3) our preliminary data from a pilot RCT in critically ill patients with sepsis demonstrate that a single 2 μ g IV dose of 1,25D increases leukocyte mRNA expression of IL-10 and HO-1,¹⁴ which are important antiinflammatory proteins that prevent AKI in animal models.

[figure not shown]
FDA status of 1,25D (calcitriol)

1,25D is available for use in patients as calcitriol, and is currently FDA-approved for the treatment of hypocalcemia in patients undergoing chronic renal dialysis.

D. Justification of dosing regimens

Overview of dosing regimens

Dosing regimens are shown in **Figure 2**. Participants assigned to 25D will be administered a liquid formulation of calcifediol, either orally or via naso/orogastric tube, at a dose of 400µg on day 0 (the day of enrollment) and 200µg on days 1, 2, 3, and 4. Participants assigned to 1,25D will be administered a liquid formulation of calcitriol, either orally or via naso/orogastric tube, at a dose of 4µg daily on days 0, 1, 2, 3, and 4. Participants assigned to placebo will be administered medium chain triglyceride (MCT) oil.

Rationale for dose of 25D

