The dosing regimen of calcitriol planned in the current study (4 µg daily for 5 days) represents a dose far lower than dosing regimens that have been used safely in prior studies, and thus is very unlikely to cause hypercalcemia or other adverse events.

G. Rationale behind the proposed research, and potential benefits to patients/society

Despite compelling data from the pre-clinical and epidemiologic studies discussed above, it remains unknown whether administration of vitamin D metabolites (25D or 1,25D) to critically ill patients will have beneficial effects on acute kidney injury (AKI) or other clinically relevant outcomes. Finding an effect of vitamin D metabolites on AKI would represent a major advance in the field, especially since currently there are no drugs or interventions that reliably prevent or treat AKI in humans. Finding a beneficial effect of vitamin D metabolites on AKI in the current study would provide preliminary data to justify a larger interventional study of vitamin D metabolites among critically ill patients, which would be powered to detect hard clinical end points such as need for renal replacement therapy and death. Finally, the current study will answer important questions about vitamin D metabolism in critically ill patients, which will inform future interventional studies of vitamin D metabolites in this and other clinical settings.

II. SPECIFIC AIMS

We will enroll 150 critically ill patients at risk of severe AKI into a 3-arm, double-blind, randomized study of calcifediol (25D), calcitriol (1,25D), or placebo to test the following:

Primary Objective – Prevention of AKI incidence/severity

Test whether administration of calcifediol (25D) or calcitriol (1,25D), compared to placebo, will decrease the incidence/severity of AKI among ICU patients, assessed by daily measurement of SCr over 7 days.

Secondary Objectives – Urinary Injury and Immune/Inflammatory Biomarkers

Test the effects of calcifediol (25D) or calcitriol (1,25D), compared to placebo, on urinary injury biomarkers (NGAL and KIM-1) and key immune/inflammatory markers assessed by monocyte mRNA expression and flow cytometry.

Tertiary Objectives – Clinical Outcomes (exploratory)

Test the effects of calcifediol (25D) or calcitriol (1,25D), compared to placebo, on ICU- and hospital length of stay, mortality, duration of mechanical ventilation, and other clinical outcomes.

III. SUBJECT SELECTION

A. Inclusion and Exclusion Criteria

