We will obtain blood samples on days 0, 1, 2, 3, 4, and 5. A summary of the volumes of blood that we will obtain at each time point is shown in **Figure 3**. On days 0 and 2 we will collect 18mL of blood, which will allow us to isolate peripheral blood mononuclear cells (PBMCs) and store them in liquid nitrogen for comprehensive analyses in the future, including flow cytometry and RT-PCR. 18mL of blood will ensure that we have a sufficient number of PBMCs to perform all of the planned analyses. Specifically, each mL of blood has approximately 10^6 PBMCs, and therefore 18mL of blood has approximately 18×10^6 PBMCs. We will aliquot and store the PBMCs as follows: aliquot #1 will have 10×10^6 PBMCs, and will be used for RT-PCR analyses on monocytes. Aliquots #2 and #3 will have 4×10^6 PBMCs each, and will be used for flow cytometry. For each of these analyses, the number of PBMCs being collected and archived represents the minimum amount necessary for the intended analyses.

In addition to the 18mL of blood on days 0 and 2 for PBMC isolation, we will also collect 2.5mL blood on days 0, 1, and 2 into PAXgene RNA tubes, which will allow us to evaluate leukocyte gene expression profiles. Finally, on days 1, 3, 4, and 5, we will collect 9mL of blood and store the plasma and DNA. 9mL of blood contains approximately 4.5mL of plasma (approximately 50% of whole blood is plasma), which will allow us to archive nine 500uL plasma aliquots at each time point. Collection of nine plasma aliquots at each time point will allow us to test the multiple hypotheses and measurements described below.

Thus, the total volume of blood that will be drawn over the course of the entire study, including PBMCs, DNA, RNA, and plasma, will be **79.5mL**. We will not enroll patients who are already enrolled in competing studies in which blood is being drawn, and we will not enroll patients with a hemoglobin level < 7 g/dl (**Table 2**). In most cases, we anticipate that blood samples will be obtained from central venous or arterial catheters by the patient's nurse. For patients who do not have a central venous or arterial catheter, blood will be obtained by venipuncture by a hospital phlebotomist, drawn concurrently with clinical blood samples whenever possible.

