The primary measurements that are anticipated to be performed on the plasma obtained from these collections will include: 25D, 1,25D, vitamin D-binding protein, heme oxygenase-1, interleukin-6, interleukin-10, thrombomodulin, parathyroid hormone, fibroblast growth factor-23, and cystatin C.

Urine

We will collect 30mL of urine at each of the above time points. In the majority of cases, urine will be collected from foley catheters placed for routine clinical care of ICU patients. Foley catheters will not be placed for research purposes. If a patient does not have a foley catheter in place for routine clinical care, urine will be collected using a bed pan, commode, or direct urination into a specimen cup. Anticipated tests that will be performed on the urine samples include neutrophil gelatinase-associated lipocalin (NGAL), interleukin 18, and kidney injury molecule-1 (KIM-1).

B. Drugs to be used

We will administer calcifediol, calcitriol, or placebo. The dosing regimens are provided in **Figure 2**. The rationale for these agents, justification of dosing regimens, and safety data are provided in sections 1C-F. Patients assigned to the placebo arm will receive medium chain triglyceride (MCT) oil, which has an identical appearance, color, consistency, and odor as calcifediol and calcitriol, both of which are also compounded in MCT oil.

Double-dummy design

Although calcifediol, calcitriol, and placebo will be identical to each other in appearance, the volumes administered will differ. For example, the concentration of calcitriol is 1 µg/ml, and therefore each 4µg dose will be administered in 4 ml. In contrast, the concentration of calcifediol is 100µg/ml. Since the first dose of calcifediol is 400µg, the first dose will also be administered in 4ml, identical to the calcifediol arm. However, calcifediol will be administered at a dose of 200µg on days 1, 2, 3, and 4 (**Figure 2**), which will be in 2ml. Therefore, to maintain blinding, we will use a double-dummy approach for drug administration on days 1, 2, 3, and 4 as follows:

Calcifediol Arm	Calcitriol Arm	Placebo Arm
Calcifediol 2ml	Calcitriol 4ml	Placebo 4ml
Placebo 4ml	Placebo 2ml	Placebo 2ml

C. Devices to be used

None

D. Procedures/surgical interventions

None

E. Data to be collected

The specific data variables that will be collected are provided in section V-A.

F. Dosing modifications

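### The urinary biomarker comparison names no adjustment for the day-0 value of the same marker or the AKI stratum, and its AUC window does not say whether day 0 is included

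*Combined protocol and SAP*

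**What the plan says.** - **Sampling (V.A, Blood samples and Urine).** "We will obtain blood samples on days 0, 1, 2, 3, 4, and 5", and for urine, "We will collect 30mL of urine at each of the above time points". Each patient is therefore planned to have six urine samples, including one from the enrolment day.
- **Dosing (I.D).** The first dose also falls "on day 0 (the day of enrollment) and" is followed by the later doses. The readable text does not say whether the day-0 urine is taken before that dose.
- **Objective (II).** The secondary objectives include effects "on urinary injury biomarkers (NGAL and KIM-1) and key immune/inflammatory markers". IL-18 is not named there but appears in VI.B.
- **End point (VI.B).** "We will also evaluate the AUC of urinary injury biomarkers, including KIM-1, NGAL, and IL-18, during the first 5 days". The scoring is to resemble that of the primary end point, in which death ranks worst, RRT next, and the remaining patients are ordered by AUC. No start day is given for the window.
- **Test (VI.C).** Secondary end points are compared "using parametric (e.g., t-test) and non-parametric (e.g., Wilcoxon Rank Sum) tests, as appropriate". No covariate, change from baseline or stratum term is named. "For secondary end points, all of which will be considered exploratory, we will consider p values <0.05 to be significant".
- **Randomisation (IV.C).** Allocation is 1:1:1, stratified by AKI present or absent at enrolment.

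**The concern.** There are two separate issues.

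1. **No baseline adjustment.** Patients enter both with and without stage 1 AKI, so entry levels of kidney injury markers plausibly vary widely. The day-0 value of the same marker and the AKI stratum are both already on record. A comparison that ignores them leaves that between-patient variation in the error term. This holds however the AUC window is read.

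2. **An undefined window.** Six samples on days 0 to 5 do not map onto a five-day window without a rule: days 0-4, 0-5 and 1-5 all fit. If day 0 is included and precedes the first dose, part of the AUC cannot carry a treatment effect. An undefined window could also be settled after the data are seen.

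At stake is the power of the trial's urinary evidence on kidney injury, with 50 patients per arm.

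**Working it through.** **The plan's own figure.** VI.D states more than 80% power for 0.62 SD with 50 per group at two-sided 2.5%. Normal approximation: 0.62 × √(50/2) = 3.10; 3.10 − 2.241 = 0.859; Φ(0.859) = 0.805. It reproduces, but it concerns only the primary end point. No power is stated for the biomarkers.

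**Inputs.** From the documents: 50 per arm, urine on days 0 to 5, two-sided 0.05 for secondary end points. Assumed, because the documents are silent: no effect on day 0, the effect size, the day-to-day correlation (0.3 to 0.7) and its pattern. Two patterns are shown: equal correlation between all days, and AR(1), where correlation decays day by day.

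**Step 1: dilution if day 0 is in the AUC.** Effect relative to the day 1-5 mean:
- Trapezoid, constant effect from day 1: (0.5×0 + 1 + 1 + 1 + 1 + 0.5) / 5 = 4.5/5 = 0.90.
- Simple mean of six days: 5/6 = 0.833.
- Trapezoid, effect rising linearly with day: (0 + 1 + 2 + 3 + 4 + 2.5) / 5 = 2.5, against a day 1-5 mean of 3; 2.5/3 = 0.833.

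So the dilution is 10 to 17%.

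**Step 2: algebra without death or RRT ranks.** With day weights w and correlation matrix R, the variance is v = w′Rw. With day 0 as covariate it is v − c², where c is the covariance of the AUC with day 0. Take an effect giving 80% power for the unadjusted day 1-5 mean (standardised effect 1.960 + 0.842 = 2.802).

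- *Equal correlation 0.5.* v = (1 + 4×0.5)/5 = 0.60; c = 0.5; adjusted variance 0.60 − 0.25 = 0.35. Power = Φ(2.802 × √(0.60/0.35) − 1.960) = Φ(1.71) = 0.956.
- *AR(1) 0.5.* v = (5 + 2×(2 + 0.75 + 0.25 + 0.0625))/25 = 0.445; c = 0.96875/5 = 0.194; adjusted variance 0.445 − 0.0375 = 0.4075. Power = Φ(2.802 × √(0.445/0.4075) − 1.960) = 0.833.
- *Unadjusted simple mean of days 0-5, equal correlation 0.5.* v = 3.5/6 = 0.583. Power = Φ(2.802 × 0.833 × √(0.60/0.583) − 1.960) = 0.658.

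Over correlations 0.3, 0.5 and 0.7, adjusted power is 0.88, 0.96 and 0.997 (equal) or 0.81, 0.83 and 0.90 (AR(1)), against 0.80 unadjusted. Unadjusted power with day 0 included is about 0.65 to 0.74.

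**Step 3: simulation with the global rank.** Log-normal marker, effect of 0.5 log SD from day 1, 12% death or RRT in the worst ranks, 50 per arm, two-sided 0.05. Power in %:

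| Correlation | Days 0-5, Wilcoxon | Days 1-5, Wilcoxon | Days 1-5, rank ANCOVA on day 0 |
|---|---|---|---|
| Equal 0.3 | 66 | 74 | 78 |
| Equal 0.5 | 54 | 65 | 75 |
| Equal 0.7 | 45 | 56 | 74 |
| AR(1) 0.3 | 78 | 83 | 83 |
| AR(1) 0.5 | 68 | 74 | 75 |
| AR(1) 0.7 | 54 | 62 | 67 |

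Type I error was 4 to 6%. Across repeated runs the covariate adds about 3 to 18 points under equal correlation and 0 to 6 under AR(1). Dropping day 0 adds 5 to 11 points in this table. The figure is about 7 to 11 if days 1-5 enter as a simple mean. The death and RRT ranks shrink the gains compared with Step 2. The AKI stratum was not simulated, so its contribution is not quantified.

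**The case against.** - **Day 0 may not be in the AUC.** A reader might infer that the plan builds the day-0 urine into the outcome. It does not say so. The primary window in VI.B runs over the days following enrolment, and V.G averages 25D over days 1 to 5, so a day 1-5 reading is at least as natural. On that reading there is no dilution. This stands, and the dilution is only conditional.
- **Day 0 may not be pre-dose.** The first dose is given the same day, and the dosing and sampling figures, which may settle the order, were not legible in the copy reviewed. This stands too. A post-dose sample would be a weaker case for a baseline covariate, so the order has to be stated.
- **Day 0 may predict little.** A reader might take the day-0 value to be the best available predictor. Nothing in the documents supports that. If the markers change fast, as AR(1) 0.3 to 0.5 represents, the covariate adds only 0 to 1 point.
- **The end points are exploratory.** VI.C says so, and no power target is set for them. That limits the importance of the point. It does not justify an open window or discarding data already collected.

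**Conclusion.** The concern holds as a precision point. The plan collects a day-0 value of each marker and stratifies on AKI, then names neither in the biomarker comparison. That omission does not depend on the reading of the window. The gain from the covariate ranges from nothing to about 18 points of power, depending on an unknown correlation and its pattern. Both patterns must be shown, because equal correlation alone would flatter the result. A further 5 to 11 points depend on day 0 otherwise being in the AUC and being pre-dose, neither of which the documents establish.

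A reader might infer that the unadjusted analysis is biased. It is not: randomisation keeps the Wilcoxon comparison valid. This is a low-severity improvement to an exploratory end point and does not touch the primary creatinine composite.

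**What to change.** In VI.B, define the biomarker AUC on days 1 to 5, give the day weights, and state that the day-0 urine is taken before the first dose, if that is so.

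In VI.C, compare each active arm with placebo by rank ANCOVA of the global rank score on treatment, the rank of the day-0 value of the same marker, and the AKI randomisation stratum. Keep the unadjusted Wilcoxon test as a sensitivity analysis. Add a simple rule for patients without day-0 urine, such as a fixed fill-in rank with a missing indicator.

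The cost is a few sentences. The sample is already planned, the assays are already anticipated and the stratum is already recorded, so no patients, visits or specimens are added. The wording should be fixed before unblinding.
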